6.1. Study Intervention(s) Administered

All participants will be required to take 4 tablets by mouth every day for 12 weeks to ensure blinding.

	Arm A	Arm B	Arm C	Arm D
Intervention Name	LY3473329 and placebo	LY3473329 and placebo	LY3473329	Placebo
Dose Formulation	Tablet	Tablet	Tablet	Tablet
Dosage Levels				
LY3473329	10 mg (1 tablet, 10 mg)	60 mg (1 tablet, 60 mg)	240 mg (4 tablets, 60 mg)	0 tablets
Placebo	3 tablets	3 tablets	0 tablets	4 tablets
Frequency	QD	QD	QD	QD
Route of Administration	РО	РО	РО	РО
Authorized as defined by EU Clinical Trial Regulation	Not authorized in EU	Not authorized in EU	Not authorized in EU	Not authorized in EU

Abbreviations: EU = European Union; PO = by mouth; QD = once daily.

LY3473329 and placebo tablets will be taken orally with approximately 240 mL of water at approximately the same time, preferably in the morning, each dosing day. On specific visit days, participants will be required to not take the drug at home and follow directions provided by the site on when to take the drug after they arrive at the clinical site.

Participants should be trained to get one pill from each bottle and should do this themselves at Visit 2 under supervision.

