9.2. Analyses Sets

This table defines the analysis population and datasets for the purposes of analysis.

Population	Description
Screened	All participants who sign the ICF.
Randomized	All participants who are randomly assigned to a treatment arm.
Efficacy Analysis Set (EAS)	Data obtained during treatment period from all randomly assigned participants who are exposed to at least 1 dose of double-blind study treatment. Excludes data after discontinuation of study drug and for participants inadvertently enrolled. Participants will be included in the treatment group to which they were randomly assigned.
Full Analysis Set (FAS)	Data obtained during the treatment period from all randomly assigned participants who are exposed to at least 1 dose of intervention, regardless of adherence to intervention. Excludes data for participants inadvertently enrolled. Participants will be included in the treatment group to which they were randomly assigned.
Safety Analysis Set (SS)	Data obtained during the treatment period plus safety follow-up from all randomly assigned participants who are exposed to at least 1 dose of intervention, regardless of adherence to intervention. Participants will be included in the treatment group to which they were randomly assigned.

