2.1. Multiplicity Adjustment

Treatment comparisons will be performed for the primary objective at the full significance level of 0.05. No multiplicity adjustments will be made for the analysis of secondary and exploratory objectives.

3. Analysis Sets

This table defines the analysis population and datasets for the purposes of analysis.

Population	Description
Screened	All participants who sign the ICF.
Randomized	All participants who are randomly assigned to a treatment arm.
Efficacy Analysis Set (EAS)	Data obtained during treatment period from all randomly assigned participants who are exposed to at least 1 dose of double-blind study treatment. Excludes data after discontinuation of study drug or initiation of Lp(a) modifying medication.
Full Analysis Set (FAS)	Data obtained during the treatment period from all randomly assigned participants who are exposed to at least 1 dose of intervention, regardless of adherence to intervention or initiation of Lp(a) modifying medication.
Safety Analysis Set (SS)	Data obtained during the treatment period plus safety follow-up from all randomly assigned participants who are exposed to at least 1 dose of intervention, regardless of adherence to intervention or initiation of Lp(a) modifying medication.

Abbreviation: ICF = informed consent form.

4. Statistical Analyses

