4.1. General Considerations

Statistical analysis of this study will be the responsibility of Lilly or its designee. Some analyses and summaries described in this analysis plan may not be conducted if not warranted by data (for example, too few events to justify conducting an analysis). Additional analyses of the data may be conducted as deemed appropriate.

Unless otherwise noted, all tests will be conducted at a 2-sided alpha level of 0.05, and confidence intervals (CIs) will be calculated at 95%, 2-sided. All tests of interactions between treatment groups and other factors will be conducted at a 2-sided alpha level of 0.10.

Change from baseline will be calculated as the value of interest at the visit minus the baseline value. In general, percent change from baseline will be calculated as the value of change from baseline divided by the baseline value in 100% scale. Some specific predefined parameters may be log-transformed before statistical analysis, if deemed necessary. If the baseline value is missing for a particular variable, then the change from baseline and percent change from baseline will not be calculated.

Unless stated otherwise, statistical summaries and analyses will be conducted based on planned randomized treatment group (LY 10 mg, LY 60 mg, LY 240 mg, and placebo), regardless of the actual treatment(s) received by the participant.

For continuous measures, summary statistics will include sample size, mean, standard deviation (SD), median, minimum, and maximum for the actual, the change from baseline, and the percent change from baseline measurements. Measures that are log-transformed will be summarized by geometric mean rather than arithmetic mean and coefficient of variation rather than standard deviation. Least squares (LS) means and standard errors derived from the analysis models will also be displayed for the change from baseline measurements. For analysis of log-transformed parameters, model estimated means and standard errors on the original scale will be derived through back-transformation using the delta method from the LS means and standard errors on the natural log-scale. All baseline measures will be analyzed using an analysis of variance (ANOVA) model that has treatment group as the fixed effect. Treatment comparisons will be displayed showing the treatment difference LS means and the 95% CIs for the treatment differences, along with the p-values for the treatment comparisons.

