4.6. Safety Analyses

Unless specified otherwise, safety assessments will be guided by an estimand comparing safety of LY3473329 doses with placebo irrespective of adherence to intervention or initiation of Lp(a) modifying medications. Thus, safety analyses will be conducted using the SS (Section 3).

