4.6.2. Adverse Events

A treatment-emergent adverse event (TEAE) is defined as an event that first occurred or worsened in severity after first dose. The Medical Dictionary for Regulatory Activities (MedDRA) Lowest Level Term (LLT) will be used in the treatment-emergent derivation. The maximum severity for each LLT during the baseline period including ongoing medical history will be used as baseline severity. Events with a missing baseline severity will be treated as "mild" in severity for determining treatment-emergence. Events with a missing severity during the postbaseline period will be treated as "severe" and treatment-emergence will be determined by comparing to baseline severity.

For events occurring on the day of first taking study medication, the case report form collected information (for example, treatment emergent flag, start time of study treatment and event) will be used to determine whether the event was pre- versus post-treatment if available. If the relevant information is not available, then the events will be counted as posttreatment.

The counts and percentages of participants with TEAEs will be summarized by treatment using MedDRA Preferred Term (PT) nested within System Organ Class (SOC). Statistical comparisons will be applied at both the SOC and PT levels. Events will be ordered by decreasing frequency within SOC. The SOC will be in alphabetical order. For events that are sex-specific, the denominator and computation of the percentage will include only participants from the given sex.

An overview of the number and percentage of participants who experienced a TEAE, serious adverse event, death, discontinued from study treatment or study due to an AE, and relationship to study drug will be summarized by treatment.

The counts and percentages of patients with TEAEs by maximum severity will be summarized by treatment using MedDRA PT. For each participant and TEAE, the maximum severity for the MedDRA PT is the maximum postbaseline severity observed from all associated LLTs mapping to the MedDRA PT. The maximum severity will be determined based on the non-missing severities. If all severities are missing for the defined postbaseline period of interest, it will show as missing in the table.

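### Safety tables follow the randomized arm even where a participant took another arm's drug, with no as-treated table and no assured listing of such cases (minor, inexpensive to fix)

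*SAP*

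**What the plan says.** SAP Section 4.1 sets the default: "Unless stated otherwise, statistical summaries and analyses will be conducted based on planned randomized treatment group", and it adds "regardless of the actual treatment(s) received by the participant".

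Protocol Section 9.2 puts the same rule in the row for the Safety Analysis Set, as it does for the two efficacy sets: "Participants will be included in the treatment group to which they were randomly assigned".

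SAP Section 3 defines membership of the Safety Analysis Set by exposure: "Data obtained during the treatment period plus safety follow-up from all randomly assigned participants who are exposed to at least 1 dose of intervention". That row has no rule on treatment received.

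The SAP safety sections (4.1.2.3 and 4.6 to 4.6.7) refer only to this set or to summaries by treatment. For adverse events, for example: "The counts and percentages of participants with TEAEs will be summarized by treatment using MedDRA". The hepatic screening plots in SAP Section 4.6.7.1.1 are labelled by randomized treatment. The same section contains the one review that looks at what the participant was actually taking, and that is a case-by-case reading of profiles, not a table.

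**The concern.** A participant enters the safety set because drug was taken, but the column is decided by allocation. For efficacy this preserves the randomized comparison. For harm it means that a placebo-randomized participant who took active drug is a placebo safety case, and the reverse. Duration of exposure (SAP Section 4.6.1) is filed in the same way.

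The plan has no assured backstop. There is no as-treated safety table. The compliance summaries in SAP Section 6.3 count missed tablets, not wrong ones. Important protocol deviations are listed under SAP Section 6.5, but what qualifies is set in a separate plan, so a listing of wrong-treatment cases is not guaranteed.

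Safety carries weight in this trial. Both sample size sections say that the size was chosen to yield enough safety data, and Protocol Section 4.3 says that the doses are meant to support a benefit/risk choice for further development.

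**Working it through.** **1. Does any safety section override the default?** I read SAP Sections 3, 4.1.2.3, 4.6, 4.6.1, 4.6.2, 4.6.4, 4.6.6 and 4.6.7. None introduces grouping by treatment received, and Section 4.6.7.1.1 names the randomized treatment for its plots. The default therefore governs all safety tables, as Protocol Section 9.2 also states.

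**2. Arm sizes.** The inputs are 233 participants, allocation 1:2:2:2 and 10% dropout (Protocol Section 9.5, SAP Section 5).
- 10 mg arm: 233 / 7 = 33.3, about 33.
- Each other arm: 2 × 233 / 7 = 66.6, about 67.
- Completers: 33.3 × 0.9 = 30.0 and 66.6 × 0.9 = 59.9, which match the plan's 30 and 60.

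**3. Weight of one participant.** 1/33 = 3.0 percentage points in the 10 mg arm; 1/67 = 1.5 points in each other arm.

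**4. Direction of the error.** All rates here are assumed.
- *Placebo-active swaps.* Suppose m participants are swapped each way between two arms of 67. The expected difference shrinks by the factor 1 − 2m/67. With true rates of 2% on placebo and 10% on 240 mg, the difference of 8.0 points becomes 7.76 (m = 1), 7.52 (m = 2) or 7.28 (m = 3). The average dilution is small.
- *Active-active swaps.* Suppose one participant randomized to 10 mg receives 240 mg and has the only event. As randomized, 10 mg shows 1/33 = 3.0%; as treated it shows 0/32. The 10 mg comparison with placebo (0/67) then moves away from no difference.

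**5. Sensitivity of small counts.** These are illustrative cases, tested with two-sided Fisher's exact test. In each, one placebo-randomized participant actually took the active dose.

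| Comparison | As treated | As randomized, that participant had the event | As randomized, that participant had no event |
|---|---|---|---|
| 240 mg vs placebo | 6/68 vs 0/66, p = 0.028 | 5/67 vs 1/67, p = 0.21 | 6/67 vs 0/67, p = 0.028 |
| 10 mg vs placebo | 3/34 vs 0/66, p = 0.037 | 2/33 vs 1/67, p = 0.25 | 3/33 vs 0/67, p = 0.034 |

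The table changes materially only if the misallocated participant is also one with the event. At the assumed rate of 6/68 = 8.8%, that is roughly 1 misallocated participant in 11. With no misallocation the two groupings are identical.

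**The case against.** **The rule is deliberate.** Protocol and SAP agree, so this is an analysis choice and not a contradiction. That stands. It can also be argued that the safety estimand covers the case, since it ignores adherence and the estimands speak of adhering to the randomized treatment. The documents do not define adherence closely enough to settle this. Even on that reading, a reader of the tables would still want to see which drug preceded the event.

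**It may never happen.** Treatment is assigned centrally and dispensed through IWRS (Protocol Section 6.3 and the Schedule of Activities). No error rate is given. That stands.

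**Two stronger readings are tempting and do not hold.**
- A reader might infer that every dose-placebo safety comparison is pulled toward no difference. Step 4 shows that swaps between active doses can do the opposite.
- A reader might count bottles and turn an assumed dispensing error rate into a number of arm switches. Protocol Section 6.1 says "Participants should be trained to get one pill from each bottle", and 240 mg is made up of four 60 mg tablets. On that basis one wrong bottle gives a placebo participant at most 60 mg a day, and three of the four tablets in the 10 mg and 60 mg arms are placebo in any case. A wrong bottle is not an arm switch.

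**The information is partly captured elsewhere.** Medication errors meet the adverse event definition (Protocol Section 10.3.1). Tablets are reconciled (Protocol Section 6.4). Deaths, serious events and discontinuations due to adverse events get narratives (SAP Section 4.6.3). Concentration-safety relationships may be examined (SAP Section 4.4.2). A wrong-treatment case would not necessarily go unseen, but none of these regroups a table.

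**No safety decision rule depends on p < 0.05.** That stands as well, so the Fisher figures show sensitivity only.

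**Conclusion.** The point holds as a minor one. On the text it is certain: safety is tabulated by randomized arm whatever was taken, with no as-treated table and no assured mismatch listing. Its effect is conditional on misallocation, for which the documents give no rate and which may be zero. If it occurs, one participant is worth about 3.0 points in the 10 mg arm and 1.5 points elsewhere, and the direction of distortion depends on which arms are involved. The event counts and rates in the working are assumptions that show how fragile small counts are; they do not forecast this trial. Sample size, power, alpha and the efficacy analyses are unaffected.

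**What to change.** For the Safety Analysis Set, amend SAP Sections 3 and 4.1 in one of two ways:

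- **Preferred:** present adverse event, laboratory and exposure tables by treatment actually received, with a pre-specified rule for mixed exposure. The rule must not leave anyone who took any active drug in the placebo column. Assigning by the treatment taken on most dosing days would fail here: drug is dispensed at Visits 2, 5 and 6 (weeks 0, 4 and 8), so an error at one dispensing covers only about a third of treatment.
- **Minimum:** keep the as-randomized tables and add an as-treated sensitivity table whenever actual and randomized treatment differ for any participant.

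In either case, list every such participant with both treatments and all events. Keep the EAS and FAS as randomized.

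Record the departure from Protocol Section 9.2 in SAP Sections 1 and 4.9, which now say that there are no changes. Protocol Section 9.3.1 lets this be done in the SAP provided that it is not a principal feature of the protocol; the sponsor should state that judgement.

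The cost is SAP wording, one derived variable from the IWRS and accountability records, and one listing. The downside is that misallocated participants are no longer compared strictly as randomized in the as-treated tables.

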For categorical measures, summary statistics will include sample size, frequency, and percentages. A logistic regression model will be used to examine the treatment difference in binary efficacy outcomes with missing endpoints imputed. Fisher's exact test or Pearson's chi-square test will be used for treatment comparisons in other categorical outcomes.

Data may exist at visits where the variable was not scheduled to be collected. In these situations, data from the early discontinuation visit that does not correspond to the planned collection schedule will be excluded from the mixed model repeated measures (MMRM), analysis of covariance (ANCOVA), or logistic regression analysis, unless otherwise specified.

Endpoints that compare treatment groups based on percent change from baseline will be conducted by log-transformation of the dependent variables. Standard errors and 95% CIs will be constructed using the delta method. The LS means and standard error for each treatment,

Page 11

difference in LS means between arms, and corresponding 95% CIs will be calculated as shown in Table EKBC.4.1, where $\bar{Z}_{b.}$ is the arithmetic mean of the baseline of the log of the response, $\hat{\mu}_{\Delta Z,k}$ and $\widehat{SE}_{\Delta Z,k}$ are the estimates and standard errors of change from baseline on the log scale for treatment group k, and $\hat{\mu}_{\Delta Z,k vs R}$, $\widehat{SE}_{\Delta Z,k vs R}$, $L_{\Delta Z,k vs R}$, and $U_{\Delta Z,k vs R}$ are the estimates, standard errors, lower and upper confidence limits for the comparison of treatment group k versus placebo.

Quantity		Change from Baseline	Percent Change from Baseline
Within	Estimate	$\left[\exp\left(\hat{\mu}_{\Delta \mathbf{Z},k}\right) - 1\right]\exp(\bar{Z}_{b})$	$\left[\exp(\hat{\mu}_{\Delta \mathrm{Z},k})-1 ight] imes 100$
l reatment	SE	$\exp(\overline{Z}_{b})\exp(\hat{\mu}_{\Delta Z,k})\cdot\widehat{SE}_{\Delta Z,k}$	$\exp(\hat{\mu}_{\Delta Z,k}) \cdot \widehat{SE}_{\Delta Z,k} imes 100$
	P-value	NR	p_k
Between- Treatment	Estimate	$[\exp(\hat{\mu}_{\Delta Z,k}) - \exp(\hat{\mu}_{\Delta Z,R})] \cdot \exp(\bar{Z}_{b.})$	$(\exp(\hat{\mu}_{\Delta Z,k \ vs \ R}) - 1) \times 100$
(Treatment k vs. Reference Arm)	SE	$e^{\bar{Z}_{b}}\sqrt{e^{2\hat{\mu}_{\Delta Z,k}}\cdot\left(\widehat{SE}_{\Delta Z,k}\right)^{2}+e^{2\hat{\mu}_{\Delta Z,R}}\cdot\left(\widehat{SE}_{\Delta Z,R}\right)}$	$\exp(\hat{\mu}_{\Delta Z,k \ vs \ R}) \cdot \widehat{SE}_{\Delta Z,k \ vs \ R} \times 100$

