)	P-value	NR	$p_{\Delta Z,k \ vs \ R}$
	95% CI	Estimate $\pm \Phi^{-1}(1-\frac{\alpha}{2})$ *SE	$([\exp(L_{\Delta Z,k vs R}) - 1] \times 100, [\exp(U_{\Delta Z,k vs R}) - 1] \times 100)$

Table EKBC.4.1.	Summary of Reported	Quantities for Variables	Requiring Log-Transformation

Abbreviation: CI = confidence interval; NR = not reported; SE = standard error.

Lp(a) is a form of low-density lipoprotein that features apolipoprotein(a) (apo(a)) bound to apolipoprotein B (apoB). The mechanism of action of the drug substance is to inhibit apo(a) binding to apoB, thereby decreasing the formation of intact Lp(a) particles. In this study, Lp(a) is assessed using two distinct assays. The "apo(a) assay" assesses Lp(a) by measuring total apo(a). Apo(a) assay measurements are collected for all participants and are used to determine the Lp(a) stratification factor (<275 nmol/L, \geq 275 nmol/L). The "intact Lp(a) assay" assesses Lp(a) by measuring intact Lp(a) particles. Intact Lp(a) assay measurements are collected for all participants except those at Chinese sites.

Unless otherwise specified, all analyses conducted for primary, secondary, and exploratory endpoints involving Lp(a) will be conducted twice, once using data from the apo(a) assay and once using data from the intact Lp(a) assay. Because intact Lp(a) assay measurements are not

collected for participants at Chinese sites, such participants will be excluded from the intact Lp(a) assay analyses.

For Lp(a), only nmol/L will be reported since there is no direct conversion to conventional units. For other laboratory values, both conventional (CN) and System International (SI) units will be presented.

Details about the analyses regarding demographic and baseline characteristics, historical illnesses and preexisting conditions, treatment compliance, concomitant medications and important protocol deviations can be found in Appendices 1 through 5 (Section 6.1 through Section 6.5, respectively).

Statistical treatment comparisons will only be performed between LY3473329 and placebo. Since the trial is not adequately powered to detect differences among LY3473329 doses, comparisons across LY3473329 doses will not be performed unless otherwise specified.

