4.1.2. Analysis methods

4.1.2.1. Analysis method for efficacy estimand

Unless otherwise specified, the primary endpoint, secondary endpoints, and exploratory endpoints will be analyzed according to the efficacy estimand, which represents the efficacy had participants adhered to the randomized treatment without initiating Lp(a) modifying medications. Considered Lp(a) modifying medications are listed in Table EKBC.4.3. The assessment of efficacy measurements guided by the efficacy estimand will be conducted using the EAS (Section 3).

Table EKBC.4.3. Lp(a) Modifying Medica	tions
--	-------

Category	Medication
Lp(a)-Altering therapies	 statins PCSK9 inhibitors prescription-dose niacin mipomersen testosterone, estrogens, anti-estrogens, progestins, selective estrogen receptor modulators, or growth hormone
Excluded Treatment Medical Devices, and/or Procedures	 lipid apheresis any investigational drug, biological agent, or device other than study provided investigational product

A restricted maximum likelihood-based, mixed-effect model repeated measures (MMRM) analysis will be used to analyze continuous longitudinal endpoints. All the longitudinal observations at each scheduled postbaseline visit will be included in the analysis. The MMRM model will include the fixed class effects of treatment group (LY 10 mg, LY 60 mg, LY 240 mg, and placebo), strata (country and baseline Lp(a) stratum [<275 nmol/L, \geq 275 nmol/L as measured by the apo(a) assay]), visit, and treatment-by-visit interaction, as well as the continuous baseline value. An unstructured covariance structure will be used to model the within-participant errors. Significance tests will be based on LS means and Type III tests. If this analysis fails to converge, the following covariance structures will be tested in order:

- 1. Toeplitz with heterogeneity
- 2. autoregressive with heterogeneity
- 3. compound symmetry with heterogeneous variances
- 4. Toeplitz
- 5. autoregressive, and
- 6. compound symmetry without heterogeneous variances.

The first covariance structure that converges will be used. The Kenward-Roger approximation will be used to estimate denominator degrees of freedom.

If the data does not warrant the MMRM model, then an ANCOVA model with treatment group, strata, and the continuous baseline value will be used to analyze the continuous endpoint. Data for participants with missing values at Week 12 will be imputed using the multiple imputation

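### Table EKBC.4.1 omits the covariance between LS means from the between-arm SE and 95% CI for absolute change; the interval is too wide where this matters, and no decision rests on it

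*SAP*

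**What the plan says.** SAP 4.1 states that for endpoints compared on percent change "Standard errors and 95% CIs will be constructed using the delta method", and Table EKBC.4.1 gives the formulas in two columns.

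- **Absolute change, between treatments.** The SE is exp(mean log baseline) times the square root of a sum. The legible part of that sum, in the extracted formula code, runs "SE}_{\Delta Z,k}\right)^{2}+e^{2\hat{\mu}_{\Delta Z,R": one squared term for the dose arm plus one for placebo. The 95% CI is "Estimate $\pm \Phi^{-1}(1-\frac{\alpha}{2})$ *SE". The p-value is marked NR (not reported).
- **Percent change, between treatments.** The SE is "\exp(\hat{\mu}_{\Delta Z,k \ vs \ R}) \cdot \widehat{SE}_{\Delta Z,k \ vs \ R} \times 100", which uses the SE of the model contrast of dose k against reference R. The confidence limits and p-value also come from that contrast.

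On the model, SAP 4.1.2.1 says "The MMRM model will include the fixed class effects of treatment group (LY 10 mg, LY 60 mg, LY 240 mg, and placebo), strata", then visit and treatment-by-visit terms, "as well as the continuous baseline value". For Lp(a) endpoints only the Lp(a) stratum is dropped; country and baseline stay. On inference, the same section says "Significance tests will be based on LS means and Type III tests" and "The Kenward-Roger approximation will be used to estimate denominator degrees of freedom". It does not say how LS means are weighted over countries.

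**The concern.** The two LS means being subtracted come from one fit with common country coefficients and a common baseline slope. Errors in those shared coefficients enter both means. If every country gets equal weight, a poorly estimated effect in a small country moves all arms' LS means together, and the correlation is positive. A variance formula that simply adds the two parts then overstates the uncertainty of the difference.

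At stake is the interval around the placebo-adjusted absolute change: Lp(a) in nmol/L by both assays, and any other marker routed through this table, such as ApoB, hsCRP and the lipid profile. One table would apply two variance rules to the same pair of LS means. For a marker with a small effect, the percent-change interval could exclude zero while the absolute-change interval includes it.

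**Working it through.** **Calibration.** The plan gives no figure for this SE. Its nearest checkable figure is the power of more than 99% (SAP 5). Completers are 233 × 1/7 × 0.9 = 30.0 and 233 × 2/7 × 0.9 = 59.9. With SD 20 and difference 60, the standardized effect is 60 / (20 × √(1/30 + 1/60)) = 13.4 for 10 mg and 60 / (20 × √(2/60)) = 16.4 for the other doses. Power is effectively 100%, so the stated figure reproduces. It does not use the disputed formula.

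**Algebra.** Write a = exp(mu_k), b = exp(mu_R), and Zb for the mean log baseline. Holding Zb fixed:

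- SAP: `SE = exp(Zb) × √(a²·SE_k² + b²·SE_R²)`
- Delta method: `SE = exp(Zb) × √(a²·SE_k² + b²·SE_R² − 2ab·Cov)`

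The contrast SE in the percent-change column satisfies `SE_kvsR² = SE_k² + SE_R² − 2·Cov`, so `Cov = (SE_k² + SE_R² − SE_kvsR²)/2`. When a = b, the delta-method version collapses to exp(Zb)·a·SE_kvsR, in line with the percent-change column. The SAP version gives exp(Zb)·a·√(SE_k² + SE_R²) instead. The two agree only if Cov = 0.

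**Size.** With equal arm SEs (60 mg or 240 mg against placebo), r = a/b and correlation ρ between the LS means, the SAP SE divided by the correct SE is `√[(1 + r²)/(1 + r² − 2rρ)]`. The residual SD cancels.

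- ρ = 0.22, r = 0.4: √(1.16/0.984) = 1.09. At r = 1: √(1/0.78) = 1.13.
- ρ = 0.38, r = 0.4: √(1.16/0.856) = 1.16. At r = 1: √(1/0.62) = 1.27.

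The correlation depends on country sizes and LS-mean weights, which the documents do not give. The values below come from ANCOVA design matrices (arm, country, baseline; one visit) with assumed layouts and randomization stratified by country.

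| Assumed layout, 60 or 240 mg vs placebo | ρ | Ratio, 60% reduction | Ratio, no effect |
|---|---|---|---|
| Observed-margin LS means, any layout tried | −0.007 to −0.001 | 0.998-1.000 | 0.996-0.999 |
| 5 or 10 equal countries, equal weights | 0.004-0.012 | 1.001-1.004 | 1.002-1.006 |
| 10 unequal (60 down to 4 participants), equal weights | 0.22 | 1.09 | 1.13 |
| 12 very unequal (70 down to 2), equal weights | 0.38 | 1.16 | 1.27 |
| 5, 10 or 15 unequal, equal weights, simulated | 0.31-0.37 | 1.13-1.16 | 1.21-1.27 |

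Other unequal layouts (8-14 countries, largest 50-70, smallest 3-5 participants) give 1.07-1.10 at a 60% reduction, and 5-8 more even countries give 1.02-1.03. In the simulated unequal layouts the 10 mg arm gives 1.12-1.14. At an 85% reduction those layouts give 1.05-1.06 for all doses.

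**Coverage.** A nominal 95% interval with SE ratio q covers 2Φ(1.96q) − 1: 96.9% at q = 1.10 and 98.1% at q = 1.20.

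**Quantile.** The t quantile is 1.987 at 88 df, 1.980 at 118 and 1.973 at 190, against 1.960. The width changes by 0.6-1.4%.

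**Mean log baseline.** Both formulas hold Zb fixed. Treating it as random adds (1 − a)²·SD²/210 to the variance, with b = 1 and 210 participants. Assuming residual log SD 0.3, 60 per arm, a = 0.4 and zero covariance, the two-term variance is 0.16 × 0.0015 + 0.0015 = 0.00174. The SE is then too small by a factor of 1.02, 1.06 or 1.12 for a log baseline SD of 0.2, 0.35 or 0.5. This acts in the opposite direction.

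**The case against.** **The cell is damaged.** In the extracted text the square on the placebo SE is missing at the end of the radicand, where a third term would sit. That loss is not counted as an error. A dropped square fits what is lost, and the notation listed with the table defines no covariance symbol, so a lost third term is unlikely. The cell should still be checked against the SAP as issued.

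**Nothing is decided on this column.** This stands. The primary and both biomarker endpoints are percent changes. The 150 nmol/L exploratory outcome is binary and analysed by logistic regression. Superiority under SAP 4.3.2 rests on p-values from the log-scale analysis.

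**Stronger readings to avoid.** A reader might infer that, with no p-value reported, this interval carries the whole inference on absolute change. It does not: exp(mu_k) = exp(mu_R) exactly when mu_k = mu_R, so the p-value in the adjacent column tests the same null. A reader might also infer that the two columns' SEs should match. One concerns a difference and the other a ratio, so only the treatment of the covariance is inconsistent. Nor do the documents support reading the error as false precision: where it is material, the intervals are too wide.

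**The size rests on assumptions.** This also stands. Country numbers and LS-mean weights are not given. Protocol 9.3.1 allows country or region, so pooling was contemplated, although SAP 4.1.2.1 says country. With even countries the error is negligible.

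**Conclusion.** The formula is wrong as written under the SAP's own method and model. That conclusion needs no assumption about countries, only that the printed cell has no third term. The size does need assumptions: under 1% with similar-sized countries or observed-margin LS means, roughly 7-16% too wide at a 60% reduction with unequal countries and equal-weight LS means, and up to about 27% for a marker with no effect. Coverage from this error alone is above nominal wherever it matters. Coverage overall is less certain, because treating the mean log baseline as random pulls the other way. This is a reporting fault in a supplementary quantity, worth correcting because the correction is nearly free. The normal quantile is a minor matter of about 1%.

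**What to change.** In the absolute-change column of Table EKBC.4.1, replace the between-treatment SE with

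`exp(Zb) × √[a²·SE_k² + b²·SE_R² − a·b·(SE_k² + SE_R² − SE_kvsR²)]`, where a = exp(mu_k) and b = exp(mu_R).

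Every term is already in the table, and the formula holds under any LS-mean weighting. Switching to observed-margin LS means is not needed; it would redefine the adjusted means and is a separate choice. In the same edit, a Kenward-Roger t quantile can replace the normal quantile. State that the interval is conditional on the mean log baseline.

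The cost is one table cell, one sentence and one line of programming, with no new data and no further model output.
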